7.4.3 Laboratory Measurements

Laboratory data will be summarized for each laboratory test listed in [Attachment 9.5.1](#).

7.4.3.1 Treatment Period

Descriptive statistics (N, mean, standard deviation, median, and range) will be reported for each continuous laboratory analyte at baseline, each scheduled post-baseline time point, and endpoint for observed value as well as change from baseline. Categorical results (eg, urinalysis tests) will be summarized at each visit by treatment group using frequency and percentage. If a subject has more than one measurement at any time point, the one closest to the scheduled visit will be used in the by-visit analysis. All lab values will be presented in the data listings.

Results for glucose and lipid tests (HDL cholesterol, LDL cholesterol, total cholesterol, and triglycerides) will be presented separately by fasting status, which includes fasting only and overall (fasting, non-fasting, or unknown). The change from baseline value at endpoint for these selected laboratory parameters (ie, lipid tests, glucose, HbA1c, and insulin), will be evaluated using a nonparametric rank ANCOVA. For the comparison of each dasotraline group versus placebo group, the change from baseline at endpoint and baseline value is ranked. A linear regression will be conducted on the change from baseline ranks and baseline value rank as independent variable to produce regression residuals. Using the values of the residuals as scores, Mantel-Haenszel row mean score tests will be produced for each dasotraline group versus placebo group.

In addition, the change from baseline value at Weeks 6, 12, and endpoint for these selected laboratory parameters (ie, lipid tests, glucose, HbA1c, and insulin), will be further evaluated

321

using an ANCOVA model which includes terms for treatment, baseline binge days group, and the corresponding baseline as covariate. The LS means of treatment differences (each dasotraline group minus placebo group) and 2-sided 95% CIs will be obtained from the model.

The normal reference ranges for laboratory tests will be used to determine whether the laboratory test value is below, within, or above the normal range. Shifts from baseline to endpoint will be produced by treatment group to show the percentage of subjects with laboratory test values below, within, and above the normal range.

Criteria for Markedly Abnormal Post-baseline Laboratory Values (MAPLV) per International System of Units (SI) of selected laboratory parameters can be found in [Table 8](#). Equivalent MAPLV criteria for conventional unit are provided in [Attachment 9.5.2](#). The criterion of MAPLV is satisfied if a value falls into the markedly abnormal range at an assessed visit or if subjects have experienced at least once MAPLV in the study period. The number and percentage of subjects with a particular MAPLV at each post-baseline visit, endpoint, and during the post-baseline double-blind phase (up to and including endpoint), regardless of baseline value, will be presented by treatment group.

**Table 8 Criteria for Markedly Abnormal Post-baseline Laboratory Values (MAPLV)
(SI Unit)**

Laboratory Test	Criteria for Markedly Abnormal Status	
	Low	High
Hematology		
Hematocrit	Male: ≤ 0.37 Female: ≤ 0.32	Male: ≥ 0.60 Female: ≥ 0.54
Hemoglobin	Male: ≤ 115 g/L Female: ≤ 95 g/L	Male: ≥ 190 g/L Female: ≥ 175 g/L
RBC	$\leq 3.5 \times 10^{12}/L$	$\geq 6.4 \times 10^{12}/L$
Total WBC Count	$\leq 2.8 \times 10^9/L$	$\geq 16 \times 10^9/L$
Basophils	N/A	$\geq 10\%$ $\geq 1.6 \times 10^9/L$
Eosinophils	N/A	$\geq 10\%$ $\geq 1.6 \times 10^9/L$
Lymphocytes	N/A	$\geq 75\%$ $\geq 12.0 \times 10^9/L$
Monocytes	N/A	$\geq 15\%$ $\geq 2.4 \times 10^9/L$
Neutrophils	$\leq 15\%$ $\leq 0.42 \times 10^9/L$	$\geq 85\%$ $\geq 13.6 \times 10^9/L$
Platelet Count	$\leq 75 \times 10^9/L$	$\geq 700 \times 10^9/L$
Chemistry		
Albumin	≤ 25 g/L	N/A
ALP	N/A	$\geq 3 \times$ ULN
AST	N/A	$\geq 3 \times$ ULN

321

Laboratory Test	Criteria for Markedly Abnormal Status	
	Low	High
ALT	N/A	≥ 3 x ULN
Bicarbonate	≤ 16 mmol/L	≥ 35 mmol/L
Calcium	≤ 2.05 mmol/L	≥ 2.99 mmol/L
Chloride	≤ 90 mmol/L	≥ 118 mmol/L
Creatinine	N/A	≥ 176.8 μmol/L
Glucose (fasting)	≤ 2.22 mmol/L	≥ 9.71 mmol/L
Inorganic Phosphorus	≤ 0.5 mmol/L	≥ 1.7 mmol/L
Magnesium	≤ 0.6 mmol/L	≥ 1.15 mmol/L
Potassium	≤ 3 mmol/L	≥ 6 mmol/L
Sodium	≤ 126 mmol/L	≥ 156 mmol/L
Total Bilirubin	N/A	≥ 34.2 μmol/L
Total Protein	≤ 45 g/L	≥ 100 g/L
Uric Acid	Male: N/A Female: N/A	Male: ≥ 625 μmol/L Female: ≥ 506 μmol/L
Urea (BUN)	N/A	≥ 11 mmol/L
Lipids panel		
Total Cholesterol (fasting)	N/A	≥ 7.77 mmol/L
LDL Cholesterol (fasting)	N/A	≥ 5.18 mmol/L
HDL (fasting)	≤ 1.036 mmol/L	N/A
Triglycerides (fasting)	N/A	≥ 3.39 mmol/L
HbA1c	N/A	≥ 7.5%
Urinalysis		
Urine Blood	N/A	≥ 1+
Urine Glucose	N/A	≥ 3+
Urine Ketones	N/A	≥ 2+
Urine Protein	N/A	≥ 2+

Note: ULN = Upper Limit of Normal; N/A = Not Applicable

A listing of subject data for those who have experienced at least once post-baseline MAPLV during the double-blind treatment period will be generated. Urine drug screen results will be presented for each parameter by visit and at endpoint. Number and percentage of positive and negative results will be displayed. Summary statistics of laboratory outputs will be generated per conventional units and International System of Units (SI), separately.

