To control the overall type I error rate strongly at 5% for the primary and key secondary endpoints, for the hypotheses to be tested (see [Section 15.2](#)), a sequential testing strategy will be used. Following the fixed sequence closed testing procedure provided in [Figure 2](#), testing will only proceed conditional on the statistical significance of the test(s) of prior level(s) at a 2-sided 5% significance level.

Safety Analyses:

Safety data will be analyzed by treatment group based on the Double-blind (DB) Safety population (for data up to the end of treatment period) and Withdrawal safety population (for data collected during the withdrawal period), separately, as appropriate.

Overall AEs (or SAEs) and AEs (or SAEs) leading to discontinuation will be summarized by system organ class, preferred term, and treatment group by presenting the number and percentage of subjects with each AE.

Descriptive statistics will be provided by visit and treatment group for observed values or changes from baseline of the safety variables. The change from baseline value at endpoint for selected laboratory parameters (eg, hemoglobin A1c, fasting glucose, fasting total cholesterol, fasting triglycerides, fasting HDL cholesterol, and fasting LDL cholesterol) will be evaluated using an ANCOVA model with terms for treatment and baseline binge days group, and corresponding baseline as covariate or nonparametric rank ANCOVA, as appropriate. A similar MMRM model as for the primary efficacy variable (with the corresponding baseline) will be applied to compare dasotraline with placebo for the following safety variables: change and percent change from baseline in body weight (kg); and change and percent change from baseline in BMI. Frequency and severity of suicidality using the C-SSRS will be summarized by treatment for the post-baseline treatment period and for the withdrawal period, separately.

CSSA total score, DESS total score, MADRS total score, and HAM-A total score will be summarized by presenting descriptive statistics of actual values and change from Week 12/EOT by treatment and

visit for the withdrawal period.

All PK data will be summarized descriptively by visit and treatment group.

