- ^m Body mass index (BMI) at screening will be calculated by the clinical site using BMI table or the BMI formula provided (Section 27, Appendix VIII). BMI on all other visits will be derived within the Electronic Data Capture (EDC) system.
- ⁿ Subjects who answer “yes” to “suicidal ideation” item 4 (active suicidal ideation with some intent to act, without specific plan) or item 5 (active suicidal ideation with specific plan and intent) on the C-SSRS assessment at Screening (in the past month) must be referred to the Investigator for follow up evaluation.
- ^o Untoward medical occurrences that occur prior to the first dose of study drug will be collected as pre-treatment events.
- ^p Subjects must be fasting for at least 8 hours (may have water and study drug) prior to the indicated laboratory tests. Visits should be scheduled in the morning.
- ^q The date and time of the last 3 doses of study drug prior to PK blood sample collection are to be recorded in the source documents and the CRF.

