11.8.1.1. Baseline: Visit 2 (Day -1)

The Baseline visit should be scheduled in the morning. Subjects must be fasting for at least 8 hours (may have water only) prior to the indicated laboratory tests. The following study related procedures will be performed:

- Review inclusion/exclusion criteria
- Record concomitant medications
- Perform physical and neurological examinations
- Collect vital signs and weight
- Perform ECG
- Clinician review of binge eating diary
- Administer scales:
 - Y-BOCS-BE
 - EDE-Q modified
 - SDS
 - MADRS (with SIGMA)
 - C-SSRS
 - BE-CGI-S
 - HAM-A (with SIGH-A)
- Collect samples for hematology, serum chemistry, fasting lipid panel, hemoglobin A1c level, insulin, hs-CRP, urinalysis, UDS, urine pregnancy test for females of child-bearing potential

- Collect blood samples for biomarkers and genotyping
- Perform breath alcohol test
- Randomization
- Dispense study medication
- Binge eating diary training

Subjects will complete the daily binge eating diary each day until the next clinic visit.

11.8.2. Week 1 (Day 7 [\pm 2 days]): Visit 3

The following study related procedures will be performed:

- Record concomitant medications
- Collect vital signs and weight
- Record AEs
- Clinician review of binge eating diary and retraining
- Administer scales:
 - C-SSRS
- Perform study medication accountability
- Dispense study medication

Subjects will complete the daily binge eating diary each day until the next clinic visit.

11.8.3. Week 2 (Day 14 [\pm 2 days]): Visit 4

The following study related procedures will be performed:

- Record concomitant medications
- Collect vital signs and weight
- Record AEs
- Clinician review of binge eating diary
- Administer scales:
 - Y-BOCS-BE
 - C-SSRS
 - BE-CGI-S
- Collect blood sample for plasma PK levels
- Perform study medication accountability
- Dispense study medication

Subjects will complete the daily binge eating diary each day until the next clinic visit.

11.8.4. Week 3 (Day 21 [\pm 2 days]): Visit 5

The following study related procedures will be performed:

- Record concomitant medications
- Collect vital signs and weight
- Record AEs
- Clinician review of binge eating diary and retraining
- Administer scales:
 - C-SSRS
- Perform study medication accountability
- Dispense study medication

Subjects will complete the daily binge eating diary each day until the next clinic visit.

11.8.5. Week 4 (Day 28 [\pm 2 days]): Visit 6

The following study related procedures will be performed:

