15.4.2.2. Clinical Laboratory Assessments

Treatment Period

Laboratory data will be summarized by presenting descriptive statistics of actual values and changes from baseline and shift tables. The number and percentage of subjects with markedly

abnormal post-baseline values for selected parameters will be presented. Individual subject listings of laboratory data also will be provided.

The change from baseline value at endpoint for selected laboratory parameters (eg, hemoglobin A1c, fasting glucose, fasting total cholesterol, fasting triglycerides, fasting HDL cholesterol, fasting LDL cholesterol, fasting insulin, and hs-CRP) will be evaluated using an ANCOVA model with terms for treatment and baseline binge days group, and corresponding baseline as covariate or nonparametric rank ANCOVA, when appropriate.

Withdrawal Period

Laboratory data will be summarized by presenting descriptive statistics of actual values, change from baseline, and changes from Week 12/EOT by treatment.

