During the study and prior to database lock, the treatment assignments for all subjects are provided to the Bioanalytical Contract Research Organization (CRO) to facilitate plasma PK sample handling and analysis. No PK samples are analyzed for placebo subjects.

Protocol and IRT Amendment for Stratification Factor of Region

For this US study, there is no concern of ‘region’ difference for treatment effect. Sponsor’s initial intention of including stratification factor of region was to provide an optimization approach to ensure a balanced treatment assignment within each region. It should be noted that stratification by region was not implemented in study SEP360-221, which is also a US study with a similar study design.

The study team noticed on July 20, 2017 that the stratification by region was not implemented as planned, ie, the initiated sites in IRT were linked to incorrect regions (See [Section 6.1.5.1](#) for details). As of July 20, 2017, among 50 planned sites of this study, a total of 44 sites were screening subjects; and 137 subjects from 35 sites had already been randomized. Due to the ‘random’ nature of the incorrect assignment of region according to the root cause of this incident, the study team decided to remove stratification criteria related to ‘region’ to minimize the impact of this mistake. Stratification criteria were amended in study protocol V3.00 and randomization is to be balanced using only permuted blocks with baseline number of binge eating days per

321

week (3 – 4 binge eating days per week, > 4 binge eating days per week).

4. Changes in Planned Analyses

There is not any change made in this SAP from the analyses planned in the protocol.

5. Efficacy and Safety Variables

[Section 6.1.2](#) provides definitions of DB Baseline and Withdrawal Baseline. For the sake of simplicity, hereafter, Baseline and DB Baseline will be used in an interchangeable way.

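### SAP 7.4.3.1 drops the protocol's hs-CRP comparison, gives insulin no fasting basis and lists an insulin ANCOVA at Week 6, when none is scheduled, while the SAP declares no change from the protocol

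*SAP*

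**What the plan says.** **Protocol.** Section 15.4.2.2 compares the arms on change from baseline at endpoint for selected laboratory parameters, by ANCOVA or, when appropriate, rank ANCOVA. Its list ends: "fasting LDL cholesterol, fasting insulin, and hs-CRP) will be evaluated using an ANCOVA model". Table 2 schedules insulin and hs-CRP at Baseline and Week 12/EOT only. The visit lists agree: the Baseline draw (Section 11.8.1.1) includes "hemoglobin A1c level, insulin, hs-CRP, urinalysis, UDS", the Week 12/EOT draw (Section 11.8.9) also includes both tests, and the Week 6 draw (Section 11.8.6) includes neither. The insulin row of Table 2 carries the footnote "Subjects must be fasting for at least 8 hours (may have water and study drug) prior to the indicated laboratory tests".

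**SAP.** Section 7.4.3.1 plans two between-arm analyses. For the rank ANCOVA it says: "The change from baseline value at endpoint for these selected laboratory parameters (ie, lipid tests, glucose, HbA1c, and insulin), will be evaluated". It then adds an ANCOVA of "the change from baseline value at Weeks 6, 12, and endpoint for these selected laboratory parameters (ie, lipid tests, glucose, HbA1c, and insulin". On fasting it says: "Results for glucose and lipid tests (HDL cholesterol, LDL cholesterol, total cholesterol, and triglycerides) will be presented separately by fasting status". Section 4 says: "There is not any change made in this SAP from the analyses planned in the protocol".

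**The concern.** The protocol names two analytes that the SAP then treats differently, and the SAP does not record the difference. Three things follow.

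- The named hs-CRP comparison with placebo would not be produced.
- Insulin, which depends on recent food intake, would be compared with no stated fasting basis, although the protocol calls for fasting insulin and the drug is one that reduces appetite.
- A Week 6 insulin contrast is listed where no Week 6 insulin sample is scheduled.

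If these are settled only after unblinding, choosing fasting-only insulin or adding hs-CRP would look post hoc.

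**Working it through.** No sample size, power or error rate is involved. The check compares lists and schedules.

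**Step 1: analytes compared between arms.** Protocol 15.4.2.2 names HbA1c, glucose, total cholesterol, triglycerides, HDL, LDL, insulin and hs-CRP, which is 8. SAP 7.4.3.1 names the 4 lipid tests, glucose, HbA1c and insulin, which is 7, and introduces both lists with ie. The difference is 8 − 7 = 1 analyte, hs-CRP. It is absent from the rank ANCOVA and from the ANCOVA.

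**Step 2: fasting basis.** Protocol 15.4.2.2 attaches fasting to 6 analytes: glucose, the 4 lipids and insulin. The SAP split covers 5: glucose and the 4 lipids. The difference is 6 − 5 = 1 analyte, insulin.

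**Step 3: sampling times.**

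| Analyte | Scheduled (Table 2) | SAP ANCOVA times |
|---|---|---|
| Insulin | Baseline, Week 12/EOT | Weeks 6, 12, endpoint |
| hs-CRP | Baseline, Week 12/EOT | none |

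Scheduled Week 6 insulin samples per arm: 0.

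**Step 4: what could fill a Week 6 insulin model.** SAP Table 4 relabels the early-termination visit and includes laboratory data in its scope. When the last scheduled visit was Week 4, the early-termination visit becomes Week 6. Unscheduled visits are kept out of by-visit analyses (SAP 6.1.4.1). So the Week 6 insulin model is either empty or consists only of subjects who stopped between the Week 4 and Week 6 visits. Neither gives a usable Week 6 treatment difference.

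**Step 5: can a fasting bias be sized?** Suppose true fasting means are equal, a fraction p of endpoint samples is non-fasting in each arm, and non-fasting insulin is r times fasting. The spurious difference, as a fraction of the fasting mean, is (p_active − p_placebo) × (r − 1). The documents give neither p nor r. The expression is zero if everyone fasts, or if the arms have equal non-fasting rates. No number follows.

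What the documents do show is that early-termination samples may be a large share of endpoint data. The sample size allows for (160 − 96)/160 = 40% discontinuation, and SAP 6.1.3.1 defines endpoint as the last non-missing post-baseline value in the treatment period.

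**The case against.** **The protocol list is illustrative.** It opens with eg, and the synopsis version stops at "fasting triglycerides, fasting HDL cholesterol, and fasting LDL cholesterol) will be evaluated using an ANCOVA model", naming neither insulin nor hs-CRP. The safety endpoint in Section 6.4 gives no week, no fasting condition and no between-arm test. This stands as a limit on severity. It does not remove the mismatch: Section 15.4.2.2 names both analytes, and the SAP closes the list while declaring no change.

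**The analytes are not lost.** SAP 7.4.3.1 gives descriptive statistics for continuous laboratory analytes, and insulin is still compared at Week 12 and endpoint. Whether hs-CRP is summarised depends on Attachment 9.5.1, which is not in the text available. A reader might infer that neither endpoint is analysed at all; the documents do not support that. SAP 7.4.1 calls all safety analyses descriptive, but 7.4.3.1 then specifies tests and confidence intervals, so that sentence does not explain the omission.

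**Week 6 is loose wording.** SAP 6.1.4.1 restricts by-visit analyses to the visits planned for each measurement, which would exclude Week 6 for insulin. That is a fair reading, but 7.4.3.1 names insulin and Week 6 together, and Table 4 could still put early-termination values there.

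**The tempting stronger reading** is that early stoppers give non-fasting samples and so bias the insulin comparison by a large, quantifiable amount. In its favour, the treatment-period fasting reminders appear only at Weeks 4 and 10, and early stoppers are asked back promptly. Against it, Section 13.3 sends them to the Section 11.8.9 assessments, which call for a morning visit and an 8-hour fast. The SAP is silent on insulin's fasting status; it does not say that fasting and non-fasting insulin are pooled. Nothing shows more non-fasting samples at early termination, or a difference between arms. The bias is possible but not established.

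**Conclusion.** The point holds as an undeclared departure of SAP 7.4.3.1 from protocol 15.4.2.2 in two respects, with one scheduling error besides: hs-CRP is absent from both between-arm analyses, insulin has no fasting basis, and insulin is listed at a week with zero scheduled samples. These rest on the text alone, with no assumed figures. The consequence is modest and confined to safety laboratory variables outside the multiplicity scheme: one named comparison missing, one comparison on an unspecified basis, and one contrast that is empty or rests on early terminators. No percentage bias should be claimed. The edit is still worth making, because it is specific, nearly free and changes what is reported.

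**What to change.** In SAP 7.4.3.1:

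1. Add insulin to the parameters shown for fasting samples and for all samples. Name the fasting-only result as the one that matches protocol 15.4.2.2. Keep the all-samples result beside it, because fasting status is observed after randomisation and restricting on it could itself select differently by arm.
2. Limit the insulin ANCOVA to Week 12 and endpoint.
3. Add hs-CRP at endpoint to the ANCOVA or rank ANCOVA list, as the protocol has it, or record its removal in SAP Section 4.

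Cost: SAP wording before database lock and a few extra table rows. Fasting status is already used for glucose and lipids. Non-fasting insulin values leave the fasting-only analysis, which loses some precision there.

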7.4.3.2 Withdrawal Period

Laboratory data will be summarized by presenting descriptive statistics of actual values, change from baseline, and changes from withdrawal baseline by visit and treatment.

7.4.4 ECG Evaluations

As a part of each ECG, heart rate (HR), axis, and the following intervals will be measured: RR, PR, QRS, and QT. Corrected QT intervals (QT_{cB} and QT_{cF}) values are based on the following formula:

- Bazett: $QT_{cB} \text{ (msec)} = QT \text{ (msec)} / (RR/1000)^{1/2}$
- Fridericia: $QT_{cF} \text{ (msec)} = QT \text{ (msec)} / (RR/1000)^{1/3}$

where RR will be reported in milliseconds (msec).

7.4.4.1 Treatment Period

Descriptive statistics (eg, mean, SD, median, range) for observed value and change from baseline values by visit and endpoint will be displayed for continuous variables (ie, HR, QRS, QT_{cF}, etc). In addition, 95% CIs of the mean change from baseline value will be provided for post-baseline visits.

The overall ECG assessment is conducted by central reading and a determination is made whether the reading is normal (or absent if applicable) or abnormal). Shifts from baseline to post-baseline visit and endpoint will be produced by treatment group.

Bazett and Fridericia corrected QT_c values will be classified as having QT_c prolongation according to [Table 9](#).

Table 9: – QTc Prolongation

QTc Prolongation
> 450 msec for males
> 470 msec for females
> 480 msec
> 500 msec
Increase from baseline QT _c ≥ 30 msec
Increase from baseline QT _c ≥ 60 msec

The number and percentage of subjects having a QT_c prolongation using any of the two correction methods (Bazett, Fridericia) by baseline, post-baseline visits, endpoint, and any post-baseline measurement (ie, the worst case in DB period) will be summarized by treatment group. A listing of ECG data for subjects with at least one prolonged QT_c will also be produced.

For other ECG parameters, subjects are classified as normal or abnormal using the limits specified in [Table 10](#). For abnormal ECG parameter reporting, counts and percentages of subjects will be presented for baseline, each post-baseline visit, endpoint, and any post-baseline DB visit (the worst case) by treatment group.

Table 10: – Definition of Abnormal ECG Values by Parameter

ECG parameter	Abnormally Low	Abnormally High
---------------	----------------	-----------------

321

(unit)		
HR (bpm)	≤50	≥100
PR interval (msec)	N/A	≥210
QRS interval (msec)	N/A	≥120
QT interval (msec)	N/A	> 500

Note: N/A = Not Applicable

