squares [LS] mean change from baseline: -16.51 vs -13.9; $P = .074$). Notably, the dasotraline 6 mg/day group was statistically superior to placebo on the ADHD-RS-IV at the Week 4 ($P = .027$), Week 6 ($P = .019$), and Week 8 ($P = .037$) timepoints (non-adjusted p-values). Statistically significant improvement on the CGI-S was also observed for the 6 mg/day group at Weeks 4 and 6, as well as at the Week 8 study endpoint ($P = .011$). The dasotraline 4 mg/day group did not show improvement relative to placebo on the ADHD-RS-IV and CGI-S assessments at the Week 8 study endpoint.

Consistent with DNRI pharmacology, the most frequent adverse events (AEs) reported in these ADHD studies were insomnia, decreased appetite, and dry mouth. In addition, significant dose dependent decreases were observed in appetite and weight. Increases in mean supine and standing heart rate (HR) observed during treatment and follow-up were generally dose dependent.

A recently completed 12-week, randomized, double-blind, placebo-controlled, flexibly-dosed, study (SEP360-221) of dasotraline (4, 6, or 8 mg/day) in adults with BED showed significant reduction in the number of binge eating days/week compared to placebo at Week 12 ($P < .0001$) with an effect size of 0.74. Significant separation from placebo was observed at all weeks starting at Week 1 ($P < .0001$). In addition, dasotraline achieved significant results compared to placebo in the key secondary endpoints including improvement in the BE-CGI-S ($P < .0001$, effect size = 0.95); reduction in the Yale-Brown Obsessive Compulsive Scale Modified for Binge Eating (YBOCS-BE) score ($P < .0001$, effect size = 0.96); and a greater number of subjects achieving 4-week cessation from binge eating ($P < .0001$; effect size = 0.66). The highest incidence of AEs for subjects receiving dasotraline ($\geq 5\%$) in descending order were insomnia, dry mouth, decreased appetite, anxiety, nausea, decreased weight, headache, dizziness, irritability, dyspepsia, constipation, thirst, and diarrhoea. There were no deaths in this study and 1 serious adverse event (SAE) was reported (suicidal ideation). There were no clinically important changes in vital signs or electrocardiograms (ECG) observed except for a mild increase in pulse rate and orthostatic pulse rate, consistent with the known pharmacology of dasotraline.

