27. Subject is known to have tested positive for human immunodeficiency virus (HIV).
28. Subject has a clinically significant abnormality on screening evaluation including physical examination, vital signs, ECG, or laboratory tests that the Investigator considers to be inappropriate to allow participation in the study.
29. The subject's screening ECG shows a corrected QT interval using Fridericia's formula (QTcF) of ≥ 450 msec for male subjects or ≥ 470 msec for female subjects. Eligibility will be based on the core laboratory ECG interpretation report.
30. Subject has any life-time history of abuse or diversion of stimulants.
31. Subject has a history of allergic reaction or has a known or suspected sensitivity to any substance that is contained in the study drug formulation.
32. Subject who in the opinion of the Sponsor and Investigator has any other psychiatric or medical condition or disorder or any other psychosocial or work-related issue not previously listed that could interfere with the diagnosis of BED at screening or subsequent evaluations during the course of the study.
33. Subject who may experience or who is currently experiencing significant psychosocial or environmental stressors (eg, loss of employment, loss of housing, financial hardship, divorce) that could impede their ability to adhere to protocol requirements, as judged by the Investigator.

34. Subject is currently participating in or has participated in any clinical trial within the last 90 days or has participated in more than 2 clinical trials within the past year. This includes studies using marketed compounds or devices.
35. Subject has previously been enrolled in a clinical trial of dasotraline (SEP-225289).
36. Subject is an investigational site staff member or the relative of an investigational site staff member.
37. Subject has started a new physical training/exercise program for the purpose of managing his or her weight or binge eating within 3 months prior to screening. Note. Subjects participating in a stable physical training/exercise program for longer than 3 months are permitted to enroll.
38. Subject has a history of malignancy within 5 years prior to the Screening visit, except for adequately treated basal cell or squamous cell skin cancer or in situ cervical cancer. History of a pituitary tumor, whether benign or malignant, is exclusionary.

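### SAP 7.4.4.1: a QTc prolongation count pooled over Bazett and Fridericia can rise with heart rate alone and hides the QTcF count; tabulate the two methods separately, QTcF first

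*SAP*

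**What the plan says.** SAP 7.4.4 defines QTcB as QT divided by the square root of RR in seconds, and QTcF as QT divided by its cube root. SAP 7.4.4.1 then says that "Bazett and Fridericia corrected QT_c values will be classified as having QT_c prolongation according to" Table 9. That table holds absolute limits ("> 450 msec for males", above 470 msec for females, above 480, above 500) and change limits ("Increase from baseline QT _c ≥ 30 msec", and the same at 60 msec). The summary by treatment group is of subjects with QTc "prolongation using any of the two correction methods (Bazett, Fridericia) by baseline, post-baseline visits, endpoint, and any post-baseline measurement". A listing covers subjects with a prolonged value.

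Protocol 4.2 says of the ADHD studies: "Increases in mean supine and standing heart rate (HR) observed during treatment and follow-up were generally dose dependent". Of the flexible-dose BED study it reports "no clinically important changes in vital signs or electrocardiograms (ECG) observed except for a mild increase in pulse rate" and in orthostatic pulse rate. Exclusion criterion 29 in Protocol 8.2 rests on a "corrected QT interval using Fridericia's formula (QTcF) of" at least 450 msec in men or 470 msec in women. QTcB has no entry limit.

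**The concern.** The two corrections differ only in how they adjust for heart rate. If a subject counts when either one is over the limit, the count follows whichever correction gives the higher value, and above 60 bpm that is always Bazett. Protocol 7.3.1 describes a fixed-dose comparison of two doses with placebo, intended to show dose response. If heart rate rises with dose, the pooled count can rise with dose while QTcF stays where it was.

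Two things are at stake. A reader could take a heart-rate effect for a repolarization effect. And because no count per method is specified, the table does not show how many subjects crossed a limit on QTcF, so any real QTcF excess would sit unseen among the Bazett flags.

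**Working it through.** The documents give no QTc outlier rate and no size for the heart-rate increase, so there is no stated figure to reproduce.

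**Step 1: relation between the corrections (SAP 7.4.4).** With RR in msec and HR = 60,000/RR:

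QTcB/QTcF = (RR/1000)^(−1/2) ÷ (RR/1000)^(−1/3) = (RR/1000)^(−1/6) = (HR/60)^(1/6).

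The ratio exceeds 1 whenever HR is above 60. On such an ECG, any absolute limit passed by QTcF is also passed by QTcB, so pooled and QTcB counts coincide.

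**Step 2: size at fixed QTcF.**
- QTcF 420 msec: QTcB is 420 × 1.0134 = 425.6 at 65 bpm, 420 × 1.0491 = 440.6 at 80 bpm, and 420 × 1.0889 = 457.3 at 100 bpm.
- A man with QTcF 430 passes 450 on QTcB above 60 × (450/430)^6 = 78.8 bpm.
- A woman with QTcF 450 passes 470 on QTcB above 60 × (470/450)^6 = 77.9 bpm.
- From 70 bpm with QTcF 400 to 420, a rise of 5 bpm adds about 5 msec to QTcB and a rise of 10 bpm adds 9 to 10 msec. Heart rate alone adds 30 msec only at about 105 to 107 bpm, and 60 msec only above about 150 bpm.

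**Step 3: simulated rates.** From the documents: three scheduled on-treatment ECGs (Weeks 4, 8 and 12 in the Schedule of Assessments), the Table 9 limits, the QTcF entry criterion, and 160 subjects per group. Assumed: 80% women; mean QTcF 412 msec in women and 402 in men, between-subject SD 15; mean heart rate 70 bpm, between-subject SD 8; within-subject SDs 10 msec and 8 bpm; QTcF independent of heart rate and unaffected by drug. Worst of three readings, percent of subjects:

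| Heart-rate shift (bpm) | 0 | +3 | +5 | +8 | +10 |
|---|---|---|---|---|---|
| Sex-specific limit, pooled | 4.4 | 5.8 | 6.8 | 8.7 | 10.2 |
| Sex-specific limit, QTcF only | 0.3 | 0.3 | 0.3 | 0.3 | 0.3 |
| Increase ≥30 msec, pooled | 13.6 | 17.1 | 19.9 | 24.5 | 27.8 |
| Increase ≥30 msec, QTcF only | 4.4 | 4.4 | 4.3 | 4.4 | 4.4 |
| >480 msec, pooled | 0.8 | 1.2 | 1.5 | 2.1 | 2.5 |
| Increase ≥60 msec, pooled | 0.2 | 0.3 | 0.4 | 0.7 | 0.9 |

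The QTcF rows are flat by construction. What the simulation measures is how far the pooled rows move.

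**Step 4: range.** With within-subject SDs from 8 msec/6 bpm to 12 msec/10 bpm, a shift from 0 to +5 bpm moves the pooled sex-specific row from 2.8% to 4.7% at the low end and from 6.4% to 9.4% at the high end. The pooled ≥30 msec row moves from 5.2% to 9.9% and from 22.7% to 29.0%.

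**Step 5: in subjects, middle scenario, 160 per group.**
- Sex-specific limit: 160 × 0.0435 = 7.0 at no shift against 160 × 0.0684 = 10.9 at +5 bpm. SD of the difference: √[160 × (0.0435 × 0.9565 + 0.0684 × 0.9316)] = 4.1. By normal approximation the +5 bpm arm shows the higher count with probability about 83%.
- Increase ≥30 msec: 21.7 against 31.8, SD of the difference 6.7, probability about 93%.
- A +5 bpm arm exceeds a +3 bpm arm on the ≥30 msec row with probability about 74%.

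**The case against.** A reader might infer that the table *will* show a *false* dose-related QT signal. The documents do not support that:

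- No size is given for the heart-rate increase, so every shift in the working is assumed. Dose dependence is reported from the ADHD studies. The BED study was flexibly dosed and saw only a mild pulse increase, with no clinically important ECG change otherwise.
- Calling the signal false presumes no true QTcF effect, which the documents do not establish.
- The sentence can be read as counts under each method, since the preceding one classifies both corrected values, and Protocol 15.4.2.3 names QTcB and QTcF as separate parameters.
- The rows for ≥60 msec and above 480 msec move little at small shifts: at +5 bpm, from 0.3 to 0.6 and from 1.3 to 2.4 expected subjects per 160.
- Entry screening on QTcF alone applies equally to all arms and cannot create a dose trend.
- Nothing in the plan makes this table the main cardiac safety result. Continuous QTcF and heart rate by visit, counts of heart rate at or above 100 bpm (Table 10), central ECG shifts and the listing are also planned. SAP 7.4.1 calls the safety analyses descriptive. A pooled flag cannot drop a QTcF-positive subject.

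All of this stands, and it limits the claim. It does not repair the table. Mean QTcF summaries do not show how many subjects crossed a limit on QTcF. If counts per method were intended, the sentence does not say so, and two programmers could produce different tables.

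**Conclusion.** The point holds in a limited form. Read literally, the count is pooled. Above 60 bpm its absolute-limit rows are the QTcB count, and it can rise with dose through heart rate with no change in QTcF. That much follows from the SAP formulas and needs no assumption about the data. The size does: for +5 bpm and no QTcF effect, roughly 6 percentage points on the ≥30 msec row (19.9 − 13.6 = 6.3) and 2.5 on the sex-specific limit (6.84 − 4.35), with little movement on the ≥60 msec row. Whether this trial would show a dose order depends on a heart-rate shift that the documents do not give. This is a cheap improvement to a descriptive safety table and does not touch any efficacy conclusion.

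**What to change.** In SAP 7.4.4.1, state that the Table 9 counts and percentages (by visit, endpoint and worst case) are given separately for QTcF and QTcB. QTcF, the measure used for eligibility, leads and QTcB is supplementary. Specify no pooled flag, and have the listing identify the method by which each subject was prolonged. Both values are already derived, so no data are lost. The cost is a sentence of SAP text and extra rows in the table shell.
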